2.2. FLOW DIAGRAM

2.3. EFFECTIVENESS OUTCOMES

2.3.1.PRIMARY OUTCOMES

The primary outcome measure is the proportion developing CWP at 12 months post intervention. The primary treatment comparison is the between arm difference in the proportions of people developing CWP from baseline to 12 months.

2.3.2.SECONDARY OUTCOMES

Comparisons with appropriate hypothesis tests will be used for the secondary outcomes, pain, illness behaviour, somatic symptom reporting, sleep problems, quality of life and wellbeing, psychological distress, patient global impression of change measure and fatigue.

2.3.3.CLINICAL & SELF REPORTED ENGAGEMENT

Counts of the sessions that were completed by the participant

Completion of treatment (by mutual agreement with therapist AND at least one session (the initial assessment) has been attended; OR, participant has at least 3 sessions of CBT (including the initial assessment))

2.4. ANALYSIS

2.4.1.GENERAL PRINCIPLES

For the equivalence study, the adjusted mixed model ITT analysis will be deemed the primary analysis with an adjusted mixed model per protocol analysis as a sensitivity analysis. For the superiority study, in accordance with CONSORT guidelines, all comparative analysis will be conducted on an ITT mixed model basis with a per protocol mixed model analysis performed as a sensitivity analysis. All analyses will be governed by this comprehensive SAP which will be agreed by the Trial Steering Committee (TSC) prior to any analyses being undertaken. There will be no formal interim analyses undertaken. Unless otherwise specified, a 5% two-sided significance level will be used to denote statistical significance. Adjustments will be made for multiple testing of secondary outcomes as discussed below.

2.4.2.DATA DESCRIPTION

Characteristics of the study participants in the two treatment arms will be described using simple summary statistics for each treatment group separately and for all participants together. Descriptive statistics will include mean and standard deviation for normally distributed continuous data, median and inter-quartile range for skewed continuous data and count and percentage for categorical data. No formal statistical comparisons will be made between baseline characteristics. Outcomes will be described at the three follow-up times: 3, 12 and 24 months, using appropriate summary statistics.

2.4.3.FLOW DIAGRAM

A CONSORT flow diagram will provide the detail of the flow of trial participants, withdrawals and post-randomisation exclusions.

2.4.4.ANALYSIS OF PRIMARY OUTCOME

Primary outcome study

The primary outcome is the between arm difference in the proportions of participants developing CWP from baseline to 12 months. This comparison will be made using simple chi-squared tests at each follow-up time. Appropriate adjustment will be made for the stratification factor used in the randomisation (the number of non-pain “high-risk” factors that a participant reports at baseline) using multiple logistic regression.

The model for outcome CWP (yes or no at 12 months) will be a multiple logistic regression. The key adjustments will be for the blocking factors, the number of high-risk factors present (2 or 3 of illness behaviour score >4, somatic symptom score >2 and sleep problem score >4) and GP practice.

$\text{Logit}(p(\text{CWP})) = \text{constant} + \text{treatment effect} + \text{blocking effect} + \text{other covariate effects} + \text{random error}.$

The treatment effect will be a fixed effect. The blocking effect will comprise the number of high-risk factors present (fixed effect) and GP practice (random effect, n=16 practices).

The other covariates that will be considered in the model are: age and sex. The expectation is that these covariates will be balanced through randomisation, but they are both known to be related to the likelihood of the development of CWP. Multiple imputation (MI) analysis will be used to examine sensitivity to missing data.

After discussion at the TSC it was decided that it will not be possible to consider the therapist effect in a formal way between the two arms. Only one arm will be exposed to the therapists and even descriptive approach was disregarded as the number of participants was expected to vary widely between different therapists.

2.4.5.ANALYSIS OF SECONDARY OUTCOMES

Secondary outcomes

Comparisons with appropriate hypothesis tests will be used for the secondary outcomes, pain, illness behaviour, somatic symptom reporting, sleep problems, quality of life and wellbeing, psychological distress, patient global impression of change measure and fatigue. Appropriate adjustment will be made for the stratification factor. The baseline value of the relevant outcome variable will also be included as a covariate. Given the multiple secondary outcomes, the p-value used to denote statistical significance will reflect the multiple comparisons.

An appropriate adjustment will be made for the stratification factor as described above, the blocking effect will be addressed through including the number of high-risk factors present (fixed effect) and GP practice (random effect).

There are 8 secondary outcomes. The most conservative approach would be to use Bonferroni $p=0.05/8=0.00625$ or a family-wise error rate of $\alpha=0.0065$ (so $1-(1-\alpha)^8 = 0.05$). A less conservative approach would be to take $p=0.01$ for significance of the secondary outcomes and this was agreed as appropriate at the TSC meeting of 9 September 2016.

The models will be generalised linear models (GLM) of the appropriate family depending on the outcome variable. Most will be ordinal logistic regression or linear regression with adjustments generally as described for the primary outcome. Multiple imputation (MI) analysis will be used to examine sensitivity to missing data.

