1.2. STUDY OBJECTIVES

The primary objectives are:

We will test the hypothesis that among patients who report regional pain for which they have already sought a consultation in primary care, and who are identified as high risk of developing chronic widespread pain, a short course of telephone-delivered Cognitive Behaviour Therapy (tCBT) reduces the onset of CWP.

We will further determine the cost-effectiveness of such a preventative intervention.

We wish to find out whether, among patients identified as being at high risk of developing CWP, a short course of tCBT reduces the risk of CWP onset. We will determine during therapy/usual care (3 months after treatment/dummy treatment start date), after therapy has finished (12 months), and in the long-term (24 months) how many persons have developed CWP and whether this is different between the two treatment groups. The primary outcome is the between arm difference in the proportions of people developing CWP from baseline to 12 months. Appropriate adjustment will be made for the stratification factor used in the randomisation (the number of non-pain “high-risk” factors that a participant reports at baseline).

Secondary objectives:

We will also measure patients' overall perceptions of their condition, their quality of life, fatigue and psychological ill health, in order to get a full picture of the effects of the tCBT. Secondary outcomes will be described at the three follow-up times: 3, 12 and 24 months, using appropriate summary statistics.

Comparisons with appropriate hypothesis tests will be used for the secondary outcomes, pain,

illness behaviour, somatic symptom reporting, sleep problems, quality of life and wellbeing, psychological distress, patient global impression of change measure and fatigue. Appropriate adjustment will be made for the stratification factor. The baseline value of the relevant outcome variable will also be included as a covariate.

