1.3. STUDY DESIGN

This study is a two-arm randomised controlled trial testing a short course of tCBT against usual care. Subjects will be eligible if they are evaluated as “at high risk” of developing CWP, namely have had a primary care consultation with regional pain and at least two of: a maladaptive behavioural response to illness, a high number of somatic symptoms and/or sleep disturbance. If successful this study would provide general practitioners with an intervention option to reduce the risk of CWP development.

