1.4. SAMPLE SIZE CALCULATIONS

Our previous longitudinal study of onset of CWP (and subsequent replication) has suggested that 21% of "high risk" persons identified will develop CWP over the course of the next twelve months. Our previous data is based on persons with pain and at least 2 out of 3 other "risk factors". There are no published studies of prevention of CWP on which to base our measure of effect. However in the MUSICIAN study some subjects, although reporting CWP at the screening survey, no longer had CWP at the enrolment interview. They were however still eligible to take part, provided they had regional pain. Therefore those subjects with regional pain provide a sub-population on which to base the likely effects of the tCBT. Amongst such subjects, those who received tCBT had a reduced odds of having CWP at the end of the study OR 0.5 95% CI (0.2-1.4) compared to those in usual care.

Thus the study is powered on the ability of the current study to reduce the onset of CWP from 21% to 12%, with 90% power and a 5% significance level. We further assume, based on prior data, that 75% of persons allocated to the tCBT arm will be adherent to the intervention, and that 80% of all subjects will return the follow-up questionnaires to assess outcome.

Final Sample Size

Accordingly we require 473 subjects per arm that is a total of 946 subjects recruited. In MUSICIAN exactly 50% of those found eligible and willing to consider taking part ultimately were randomised. A previous trial of a cognitive-behavioural intervention to prevent chronic pain found that 36% of patients identified as eligible ended up being recruited to the study. If 80% of eligible patients agreed to be contacted about taking part, this equates to 45% of those eligible and willing to consider taking part being randomised - higher numbers for a clinical trial of CWP reflect the fact that this is a prevention trial rather than a treatment trial and may be less attractive to potential participants. Thus we aim to find a total of 2102 subjects who are eligible and willing to consider taking part. Assuming a participation rate to the survey of 30%, that 1 in 4 people will be "at risk", and (using data from MUSICIAN) that 80% of people who return a questionnaire agree to consider taking part, we require to survey 35,037 persons.

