Table 19: Secondary outcome adjusted analysis of QoL from ICECAP score in the tCBT and usual care arms on the ITT population

	3 Months			12 Months			24 Months		
	Adjusted coefficient	95% CI	p-value	Adjusted coefficient	95% CI	p-value	Adjusted coefficient	95% CI	p-value
Treatment: tCBT vs Usual care									
QoL from ICECAP score at baseline									
Number of high-risk factors present: 3 vs 2									
Age									
Gender									
Random effect: GP practice									

Table 20: Secondary outcome adjusted analysis of Fatigue score in the tCBT and usual care arms on the ITT population

	3 Months			12 Months			24 Months		
	Adjusted coefficient	95% CI	p-value	Adjusted coefficient	95% CI	p-value	Adjusted coefficient	95% CI	p-value
Treatment: tCBT vs Usual care									
Fatigue score at baseline									
Number of high-risk factors present: 3 vs 2									
Age									
Gender									
Random effect: GP practice									

Table 21: Secondary outcome adjusted analysis of Global impression of change measure score in the tCBT and usual care arms on the ITT population

	3 Months			12 Months			24 Months		
	Adjusted coefficient	95% CI	p-value	Adjusted coefficient	95% CI	p-value	Adjusted coefficient	95% CI	p-value
Treatment: tCBT vs Usual care									
Global impression of change measure score at baseline									
Number of high-risk factors present: 3 vs 2									
Age									
Gender									
Random effect: GP practice									

Table 22: Primary outcome presence of CWP at 3, 12 and 24 months in multilevel model in the tCBT and usual care arms on the ITT population

	Multilevel at 3 time points		
	Adjusted OR	95% CI	p-value
Treatment: tCBT vs Usual care			
3 to 12 months			
12 to 24 months			
Number of high-risk factors present: 3 vs 2			
Age			
Gender			
Random effect: GP practice			

Table 23: Secondary outcome presence of pain at 3, 12 and 24 months in multilevel model in the tCBT and usual care arms on the ITT population

	Multilevel at 3 time points		
	Adjusted OR	95% CI	p-value
Treatment: tCBT vs Usual care			
3 to 12 months			
12 to 24 months			
Number of high-risk factors present: 3 vs 2			
Age			
Gender			
Random effect: GP practice			

Table 24: Secondary outcome illness behaviour score at 3, 12 and 24 months in multilevel model in the tCBT and usual care arms on the ITT population

	Multilevel at 3 time points		
	Adjusted coefficient	95% CI	p-value
Treatment: tCBT vs Usual care			
3 to 12 months			
12 to 24 months			
Illness behaviour score at baseline			

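### The SAP names a primary analysis only for a non-existent equivalence study, and does not say whether the chi-squared test or the adjusted logistic model decides the 12-month comparison

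*SAP*

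**What the plan says.** SAP section 2.4.1 contains the plan's only use of the term primary analysis: "For the equivalence study, the adjusted mixed model ITT analysis will be deemed the primary analysis". The sentence after it deals with superiority and names no single model: "For the superiority study, in accordance with CONSORT guidelines, all comparative analysis will be conducted on an ITT mixed model basis".

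The rest of the SAP describes one superiority trial. Section 1.3: "This study is a two-arm randomised controlled trial testing a short course of tCBT against usual care". The hypothesis in section 1.2 is that "a short course of telephone-delivered Cognitive Behaviour Therapy (tCBT) reduces the onset of CWP". The sample size in section 1.4 is for a difference, to "reduce the onset of CWP from 21% to 12%, with 90% power and a 5% significance level". No equivalence margin is given.

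Section 2.4.4 gives two methods for the 12-month comparison. The first: "This comparison will be made using simple chi-squared tests at each follow-up time". The second: "The model for outcome CWP (yes or no at 12 months) will be a multiple logistic regression", with the number of high-risk factors as a fixed effect, GP practice as a random effect, and age and sex as candidate covariates. Section 2.4.6 adds a repeated-measures mixed model over 3, 12 and 24 months and mentions generalised estimating equations as an alternative. Table 8 sets unadjusted and adjusted odds ratios and p-values side by side. Table 22 is headed "Primary outcome presence of CWP at 3, 12 and 24 months in multilevel model".

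Section 10 of the protocol lists the same three methods without ranking them, and leaves the detail to the SAP.

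**The concern.** A primary result needs one pre-specified test. Here the sentence that should name it refers to another kind of study. The sentence that assigns the primary comparison names a chi-squared test, which is not a mixed model and ignores the stratified randomisation. That does not fit the mixed-model basis that section 2.4.1 sets for superiority. The adjusted logistic model does fit it, but nothing says that this model takes precedence.

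If the two p-values in Table 8 fall on opposite sides of 5%, the plan gives no rule for declaring the result. Whoever reports the trial would choose after seeing the data, and the nominal 5% error rate would no longer be guaranteed.

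**Working it through.** **1. What the sample size implies.** Inputs from SAP 1.4: 21% versus 12%, two-sided 5%, 90% power, 80% return of questionnaires.

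- Standard two-proportion formula, with mean proportion 0.165: n = [1.960·√(2·0.165·0.835) + 1.282·√(0.21·0.79 + 0.12·0.88)]² / 0.09² = 355.4, so 356 per arm.
- With continuity correction: (n/4)·[1 + √(1 + 4/(n·0.09))]² gives 378 per arm.
- 378 / 0.80 = 472.5, so 473 per arm. This is the plan's figure.

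The trial was therefore sized on a comparison of two proportions at one visit, not on a three-visit model.

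**2. Which statements compete.**

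- *Mixed model (2.4.1) and logistic regression (2.4.4).* GP practice is random in the logistic model, so that model is a mixed model. These two statements agree.
- *Mixed model (2.4.1) and chi-squared test (2.4.4).* The chi-squared test has no random effect and no adjustment. These two conflict.
- *Unadjusted and adjusted columns of Table 8.* Both carry a p-value and neither is marked as deciding.
- *Three-visit model (2.4.6, Table 22).* It has one treatment row and no treatment-by-time row. As laid out, it does not report the 12-month effect that sections 1.2 and 2.3.1 define as primary. It is not labelled as supportive either.

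**3. Who is analysed.** Section 2.1 admits to the ITT set anyone randomised who has the primary outcome at one or more follow-ups. A person with a value at 3 or 24 months but not at 12 belongs to that set. That person contributes to the three-visit model but not to an unimputed 12-month test. Naming the model without the analysis set would leave this open.

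**4. Size of the open choice.** Simulation with no treatment effect, 2,000 trials per setting. The following are assumptions, not figures from the plan:

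- 378 complete cases per arm at all three visits, with CWP at about 21% in both arms throughout;
- modest effects of stratum, age and sex, no practice effect, and strata not balanced by design;
- latent between-visit correlation from 0.3 to 0.9;
- pooled logistic regression with cluster-robust errors standing in for the three-visit mixed model.

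Let A be rejection by chi-squared, B rejection by the 12-month logistic model, and d the proportion of trials in which they disagree. Since P(A) + P(B) = 2·P(both) + d, the chance that at least one rejects is [P(A) + P(B) + d] / 2.

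| Correlation | Chi-squared | Logistic | Three-visit | d | A or B | Any of three |
|---|---|---|---|---|---|---|
| 0.3 | 4.45% | 4.30% | 4.25% | 1.45% | (4.45+4.30+1.45)/2 = 5.10% | 7.65% |
| 0.5 | 5.10% | 4.70% | 4.50% | 1.90% | (5.10+4.70+1.90)/2 = 5.85% | 8.30% |
| 0.7 | 4.55% | 4.65% | 5.10% | 1.60% | (4.55+4.65+1.60)/2 = 5.40% | 8.15% |
| 0.9 | 4.20% | 4.40% | 4.55% | 1.10% | (4.20+4.40+1.10)/2 = 4.85% | 6.75% |

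The Monte Carlo standard error is at most about √(0.08·0.92/2000) = 0.6 percentage points. The 12-month logistic and three-visit models disagreed in 3.65% to 5.70% of trials, so most of the excess in the last column comes from the three-visit model.

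**The case against.** The best defence is that a careful reader can work out the intended analysis. The equivalence sentence looks like leftover template text. Chi-squared followed by logistic regression reads naturally as unadjusted then adjusted, which is how Table 8 is laid out. The per-protocol and multiple-imputation tables marked as sensitivity analyses (Tables 9 and 10) repeat the 12-month layout of Table 8, which points to that table as the main result. Endpoint, time point, sidedness and significance level are all stated, and section 2.1 calls intention-to-treat the main analysis.

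Most of this stands, and it narrows the point. It does not close it. The main-analysis label in section 2.1 settles the population principle, not the model. Table 8 holds both candidate p-values, so pointing to Table 8 does not choose between them. The only sentence that assigns the primary comparison to a test names the chi-squared test, against the superiority rule in section 2.4.1.

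A reader might also infer that Table 22 sets up the three-visit model as a rival primary analysis. Its title does not support that. The same primary-outcome label heads Tables 11 and 12, which cover 3 and 24 months, so it names the variable and not the deciding analysis.

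**Conclusion.** The point holds in a limited form. The equivalence sentence is wrong for this trial and is the only place where the SAP calls a model primary. For the 12-month comparison, nothing ranks the unadjusted p-value against the adjusted one, and the three-visit model is left without a stated role.

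The practical size is small to moderate. Choosing the better of the two 12-month tests raises the false-positive rate to roughly 5% to 6%, against 4.2% to 5.1% for either test alone in the same simulation. The 7% to 8% with all three is a worst case. It assumes that the best of three p-values is picked, and it depends mainly on a model that does not target the stated 12-month comparison. It should not be read as the expected error rate. All these figures rest on the simulation assumptions listed in the working.

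Two stronger readings are tempting and should not be drawn. One is that the mixed-model and logistic statements contradict each other; the random practice effect reconciles them. The other is that the wording prepares an equivalence claim from a null result. The documents state a hypothesis of reduction, size the trial for a difference and give no margin, so nothing in them supports that inference.

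**What to change.** Delete the equivalence sentence in SAP 2.4.1 and replace it with text such as:

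> This is a superiority trial. The single primary analysis is the logistic model for CWP at 12 months, with treatment, number of high-risk factors, age and sex as fixed effects and GP practice as a random effect. It includes all randomised participants with a 12-month CWP value, analysed as randomised, at two-sided 5%. Multiple imputation of missing 12-month values is a sensitivity analysis. The chi-squared comparison is descriptive and the three-visit mixed model is supportive.

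Amend section 2.4.4 to match, mark the adjusted treatment row of Table 8 as the primary result, and label Table 22 as supportive. The text settles age and sex, which section 2.4.4 lists only as candidates although Table 8 already carries both. It also settles the analysis set, which the ITT definition in section 2.1 leaves open for a 12-month test.

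The cost is SAP wording and approval by the trial steering committee before analysis. The sample size and data collection do not change. What is given up is the freedom to choose the analysis after the data are seen. People seen only at 3 or 24 months leave the primary set and enter through the supportive model and the imputation analysis.

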We have conducted prospective epidemiological studies which have demonstrated that it is possible to identify “high risk” groups. In the first study, a high risk group for CWP onset was identified on the basis of two factors: somatic awareness (using the Somatic Symptom Scale) and illness behaviour (using the Illness Behaviour Score) (15). This was replicated in a second study conducted by the applicants (16). These “aetiological models” excluded pain and therefore we have re-analysed data from the latter study (also considering pain status) to identify the best predictors of onset and which results in a model more suitable for use in prevention studies. The resulting “at risk model” requires regional pain and two of the following: maladaptive behavioural response to illness (Illness Behaviour score > 4), a high number of somatic symptoms (Somatic Symptom Score > 2) and sleep disturbance (Sleep Problem Scale Score > 4). In the second “validation” study, from a population of 2,374 persons without CWP, 653 satisfied the definition of “high risk of CWP” of whom 139 had developed CWP twelve months later (that is a Positive Predictive value of 21.3%). Amongst persons not deemed to be at high risk (n=1721), 77 developed CWP which is a Negative Predictive Value of 95.5%.

An Arthritis Research UK report on fibromyalgia/CWP, based on a think-tank held in July 2012, identified prevention as a research priority. We have previously shown short and long-term effectiveness of tCBT for CWP (compared to usual care), in an Arthritis Research UK funded study (11, 17). Specifically this demonstrated sustained improvement in patient global assessment of change, reduced psychological distress, fear of movement and reliance on passive coping styles. Secondly we have developed and refined statistical models which identify persons at high risk for the future development of CWP. We therefore now propose a study to test whether tCBT can reduce the risk of CWP onset amongst those at high risk.

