## 6.2 Timeline Flowchart

### **6.3 Recruitment**

We will mail a randomly selected sample of adults aged 25 years and over registered with participating general practices in the study areas.

The Scottish Primary Care Research Network (SPCRN) will be involved in recruitment of patients to this study from primary care. SPCRN staff provide GP practices with an expert service to undertake searches of their electronic databases to identify a random sample of potentially eligible patients and prepare the ethically approved letters to be sent out. SPCRN staff work on behalf of the healthcare team under practice staff supervision. Each member of SPCRN staff must have a current NHS substantive or honorary contract in order to carry out these activities. Searches are undertaken at each GP practice before the screening survey questionnaires are sent out by Health Informatics Centre Services in Dundee on behalf of the practice. Patients will return completed survey questionnaires to the research team at the University of Aberdeen where they will be assessed by the research team for eligibility and sent invitation letters if eligible.

The “screening questionnaire” will determine whether a) they meet the study eligibility criteria and b) they would be willing to be contacted again regarding a treatment trial for “musculoskeletal health”. The questionnaire will include:

- Pain assessed by specific questions on the experience of pain, consultation and body manikins (which will provide site and also allow us to exclude those who already have chronic widespread pain).
- Illness Behaviour Scale (18)
- Somatic Symptoms Scale (excluding pain items) (19)
- Sleep Problem Scale (20)
- Quality of Life and Wellbeing (EQ-5D-5L (21); ICECAP (22))
- General Health Questionnaire (23)
- Chalder Fatigue Scale (24)

The inclusion criteria are:

- A ‘high-risk’ profile for developing CWP as identified on the screening survey, i.e.:
  - Have pain for which they have sought consultation to primary care in the last 6 months, or have pain and report consulting a doctor frequently
  - Any 2 of the following:
    - Illness Behaviour Score > 4
    - Somatic Symptom Score > 2
    - Sleep Problem Score >= 4
- Access to a landline telephone or mobile telephone

- Ability to understand English sufficiently to participate in the intervention
- Ability to give informed consent
- Aged 25 years or over

Exclusion criteria:

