#### **6.5 Randomisation**

After consent has been given to participate in the study the researcher will contact the Trial randomisation centre at the Centre for Healthcare Randomised Trials (CHaRT) at the University of Aberdeen, using the internet or by telephone. This service is available 24 hours a day. Using a computer randomisation program, subjects will be randomly allocated into one of the two treatment groups, stratified in blocks by one predictor of outcome i.e. the number of non-pain “high-risk” factors they report (2 or 3) since this is related to the risk of CWP onset, and GP Practice. Subjects will be notified of the outcome of allocation during the consent/randomisation phone-call. If allocated to the active intervention, the participant will receive a phone call from a therapist within 3 working days to arrange an initial appointment. We will confirm the allocation to treatment arm in a letter to the participant.

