2. ANALYSIS

2.1. STUDY POPULATIONS

Comparison between arms will be on an intention-to-treat basis (main analysis) with a per protocol sensitivity analysis.

Intention to treat (ITT) population

Intention to treat analysis will be of all participants who were randomised and for whom at least one follow-up observation of the primary outcome is available. Participants will be analysed in the group to which they were randomised.

[figure not shown]
Per protocol (PP) population

Pre protocol analysis will be of all participants of the ITT population excluding participants who were not compliant with their randomised study arm. Non-compliance is defined as those not having any primary outcome data and/or those not completing treatment as in the definition below.

Full intervention will consist of an initial assessment (45-60 minutes), 6 weekly sessions (each 30-45 minutes) over six weeks, and then booster sessions at 3 and 6 months. The per protocol analysis will be those receiving the completed treatment (defined below) vs. all others.

A participant in the CBT group has completed treatment if: there is mutual agreement between therapist and participant to stop treatment AND at least one session (the initial assessment) has been attended; OR, participant has at least 3 sessions of CBT (including the initial assessment)

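### The SAP defines its stratification covariate with a sleep score above 4, while protocol eligibility counts 4 or more; the SAP should name the stratum recorded at allocation as the covariate

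*SAP*

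**What the plan says.** SAP 2.4.4 introduces the covariate with "Appropriate adjustment will be made for the stratification factor used in the randomisation" and glosses it as the number of non-pain high-risk "factors that a participant reports at baseline". Its model paragraph then gives score cut-offs: "the number of high-risk factors present (2 or 3 of illness behaviour score >4, somatic symptom score >2 and sleep problem score >4". The model statement adds "The blocking effect will comprise the number of high-risk factors present (fixed effect) and GP practice", and SAP 2.4.5 carries the same adjustment into the secondary outcomes. Tables 6 and 34 list the sleep factor as a score above 4 and have factor-count rows for 2 and 3 only. Table 8 and later model tables report the factor as 3 vs 2.

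The protocol is not uniform. Section 6.3 (inclusion criteria) has "Sleep Problem Score >= 4", and the Cohort Follow-up part of 6.6 repeats it. Section 3, describing the at-risk model, has "sleep disturbance (Sleep Problem Scale Score > 4". Section 6.5 stratifies on the number of "factors they report (2 or 3) since this is related to the risk of CWP onset" and on practice, and states no cut-offs.

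SAP 1.5 and 1.6.1 rest the SAP on protocol version 4 (26/02/2016). SAP 1.6.1 says later amendments will be checked for their impact and the SAP changed only where needed.

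**The concern.** A covariate meant to be the randomisation stratifier should reproduce the stratum in which each participant was allocated. The SAP's written rule differs from the supplied eligibility rule in one component, sleep, and at one value, a score of exactly 4. The SAP does not say whether the covariate comes from the randomisation record or is computed from questionnaire scores.

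If a programmer applies the cut-offs as written, some participants may be placed in the wrong level, or in a level that the model and tables do not have. At stake are the covariate in the primary and secondary models, its reported effect, and the baseline factor counts.

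**Working it through.** **1. The sleep cut-off, place by place**

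| Place | Sleep rule | Applies to |
|---|---|---|
| Protocol 3 | >4 | background at-risk model |
| Protocol 6.3 | >=4 | trial eligibility |
| Protocol 6.5 | none given | stratifier, 2 or 3 factors |
| Protocol 6.6, Cohort Follow-up | >=4 | people not recruited to the trial |
| SAP 2.4.4 | >4 | model covariate |
| SAP Tables 6 and 34 | >4 | descriptive rows |

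The illness behaviour (>4) and somatic symptom (>2) cut-offs agree between protocol 6.3 and SAP 2.4.4. Only sleep differs.

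**2. What the difference does to the count**

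Count = (illness behaviour >4) + (somatic symptoms >2) + (sleep factor). These are all the profiles with at least 2 factors under protocol 6.3:

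| Illness behaviour | Somatic | Sleep score | Count, sleep >=4 | Count, sleep >4 |
|---|---|---|---|---|
| yes | yes | <4 | 2 | 2 |
| yes | no | >4 | 2 | 2 |
| no | yes | >4 | 2 | 2 |
| yes | yes | >4 | 3 | 3 |
| yes | no | =4 | 2 | **1** |
| no | yes | =4 | 2 | **1** |
| yes | yes | =4 | 3 | **2** |

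Four of the seven profiles agree. The three that differ all have a score of exactly 4. With one common cut-off there are no mismatches.

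That allocation used >=4 is an inference, because protocol 6.5 gives no cut-off. It is a reasonable one: if eligibility is >=4, a stratifier counting >4 would leave some eligible people with a count of 1 and no stratum.

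**3. How many participants**

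The plan gives no figure for scores of exactly 4. As illustration only, for assumed shares of 2%, 5% and 15% of the planned 946:

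- 946 × 0.02 = 19, 946 × 0.05 = 47, 946 × 0.15 = 142 coded one level low.
- If two thirds of these have two factors (assumed), 13, 32 or 95 would have a count of 1.

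If the cut-off changed during enrolment, the share would apply to fewer than 946.

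**4. Effect on the treatment comparison**

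The score is fixed before randomisation, so any miscoding is unrelated to arm.

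Simulation inputs from the plan: 21% v 12%, and 473 × 0.80 = 378 per arm (756 in all). Assumed inputs: 40% with three factors, stratum odds ratio 1.5 or 2.5, and the shares in step 3. The logistic model had treatment and factor count; age, sex and practice were left out. There were 5,000 runs per setting, and everyone stayed in the model. The recorded stratum was compared with the >4 count, with 1 either kept as a third level or merged with 2.

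- Power differed by at most 0.3 points (for example 92.1% v 91.8%).
- The treatment odds ratio differed by at most 0.002 (for example 0.497 v 0.499).
- Significance changed in at most 0.8% of runs.

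**5. Effect on the reported 3 vs 2 odds ratio**

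In the most extreme setting (15%, true value 2.5) the mean estimate was 2.26 to 2.29, against 2.52 with the recorded stratum. The log odds ratio has a standard error of about 0.20 in this setting, so the 95% interval around 2.5 is 2.5 × exp(±1.96 × 0.20), or about 1.7 to 3.7. The shift lies well inside it.

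**The case against.** The strongest reply is that the SAP already means the recorded stratum. It names the factor used in the randomisation and speaks of blocking factors and a blocking effect. A reader might take "factors that a participant reports at baseline" as a sign of re-derivation from scores. That is weak evidence: protocol section 10 uses the same phrase for the randomisation factor itself, and protocol 6.5 also describes the stratifier as what participants report. This part of the reply stands.

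It also stands that the documents do not state two cut-offs for the stratifier. The only one written for it is the SAP's; the >=4 version is carried over from eligibility. The Cohort Follow-up criteria concern people outside the trial and say nothing direct about randomised participants.

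The versions differ too. The supplied protocol includes a COVID-19 sub-study (6.9), so it is later than the version 4 on which the SAP rests. Version 4 is not available and may have read >4. If the recorded stratum is used, leaving the SAP model unchanged is consistent with SAP 1.6.1.

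Finally, a row labelled >4 that reports scores above 4 is not wrong in itself, the SAP calls its tables examples, and a count of 1 would be visible when tabulated.

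What the reply does not remove is that no sentence tells the analyst to take the covariate from the randomisation record, while one sentence supplies a scoring rule that does not match the supplied eligibility criteria.

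**Conclusion.** The mismatch is real and minor. It is an inconsistency in the documents that becomes a coding error only if two conditions both hold: the covariate is derived by the written >4 rule, and allocation counted sleep from 4 upward. If the recorded stratum is used, the model is correct as planned and only the cut-off text and table rows need attention.

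If both conditions hold, the covariate, its reported 3 vs 2 effect and the baseline factor counts would be wrong, by an amount that the documents do not allow to be estimated. The counts and odds ratios above for assumed shares illustrate the mechanism; they do not measure its effect in this trial.

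A reader might infer that the primary comparison is biased, loses power or loses participants. The documents do not support this. Any miscoding is fixed before allocation, and the simulated changes in power and treatment odds ratio are negligible. SAP 2.1 analyses "all participants who were randomised and for whom at least one follow-up observation of the primary outcome is available", so a count of 1 is no ground for exclusion. The chi-squared test and the unadjusted treatment odds ratio do not use the covariate at all.

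**What to change.** In SAP 2.4.4 and 2.4.5, state that the covariate is the 2-or-3 stratum recorded by the randomisation centre at allocation and is not recomputed from questionnaire scores. Use that stratum for the factor-count rows of Tables 6 and 34.

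Reconcile the sleep cut-off across protocol sections 3, 6.3 and 6.6 (Cohort Follow-up), SAP 2.4.4 and Tables 6 and 34 with the protocol version under which participants were enrolled. If the cut-off changed between versions, say when. Which cut-off is right is for the trial team to settle from its own records.

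The cost is wording in the SAP, its tables and, where needed, the protocol. Allocation was already stratified on this factor, so no new data are needed and the sample size does not change.
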